6.2 Data Security

The workflow has been designed to limit access to the link between identifiers and the study ID (see Research Design, section h). Access to data will be limited to study personnel. All computers on which analyses will be conducted will be password protected and will be further protected by the Rutgers firewall and malware protection. All data will be transferred using a secure file transfer system (encrypted file, encrypted email, or secure file transfer protocol). Paper copies of raw data will not be produced. Only aggregate results will be published.

6.3 Data and Safety Monitoring – Not Applicable

6.4 Reporting Results

A. Sharing of Results with Subjects – Not Applicable

B. Individual Results – Not Applicable

C. Aggregate Results

Aggregate results will be published in scientific journals and abstracts will be presented at scientific meetings. Abstracts will be posted on the NJSCR website for the public and participants to read. Participants who request copies of scientific findings will be sent any published journal articles.

D. Professional Reporting

Investigators will also comply with policies and procedures governing the publication of finding from research utilizing NJSCR data, as well, [name] and all co-authors will be given opportunity review any abstract/manuscript prior to its submission or use.

Significant contributions to the field of genetics screening will be reported through:

- Poster and/or oral presentations submitted for professional meetings
- Summarized tables described in manuscripts for submission to professional journals such as Cancer

7.0 Data and/or Specimen Banking

A. Storage Methods – Not Applicable

B. Storage Data – Not Applicable

C. Releasing Data/Specimens – Not Applicable

8.0 Other Approvals/Authorizations

This study has approval by the University of New Mexico Comprehensive Cancer Center and the Colorado Central Cancer Registry as collaborating sites.

Genetic Risk Assessment for Cancer Education and Empowerment Project (GRACE)

NCT03326713

January 16th, 2025

GRACE Statistical Analysis Plan

Biostatisticians blinded to study arm assignment performed an intent-to-treat analysis using SAS v9.4, and RMediation package available in R. Summary statistics of baseline patient sociodemographic variables were compared among treatment arms using ANOVA and χ^2 tests. Pearson correlation coefficients were calculated to discern potential correlations between the selected theorized mediator variables. We calculated Cronbach's alpha to ensure internal consistency (the extent to which their respective items measured the same construct) across measures at baseline and the one-month follow-up.

Logistic regression was used to compare the percentage of CGRA intentions reported at the one-month follow-up between study arms; odds ratios and 95% confidence intervals (CIs) were calculated. We leveraged mixed model analysis to assess longitudinal between-treatment-arm and pre-to-post-differences in the scores for CGRA intentions and each theorized mediator variable. (The approach also accounted for repeated measures in our study design, as well as the 95% CIs, using linear contrasts.) We then performed mediation analysis to assess whether improvement in CGRA intentions was mediated by pre-to-post changes of the theorized mediator variables.

Due to the significant improvement in CGRA intentions for TCN compared to the other study arms, we studied the mediational relationships for CGRA intentions in TCN using the within-group analysis. We first conducted a single variable mediation analysis, in which only one theorized mediator was introduced into the model to assess its indirect effects on CGRA intentions. We followed this approach with multivariable mediation analysis, in which the theorized mediators were introduced into the model simultaneously to assess their indirect effects on the outcome. Specifically, we fitted the following models: Model 1.1: $Y_{it} = c_{0i} + c_1 \text{time}_{it} + e_{1it}$; Model 1.2: $M_{it} = a_{0i} + a_1 \text{time}_{it} + e_{2it}$; and Model 1.3: $Y_{it} = b_{0i} + b_1 \text{time}_{it} + b_2 M_{it} + e_{3it}$. In these models, Y_{ij} and M_{ij} represented CGRA intentions and mediator of subject i at time j ($j = 0$ for baseline and $j = 1$ for one-month post-intervention), respectively. We tested $H_0: a_1 b_2 = 0$ using the confidence interval (CI) approach. If 0 was not included in 95% CI, then we rejected H_0 and established the mediation relationship. The percentage of indirect effect for significant theoretical intervention variables was calculated as $P_M = a_1 b_2 / c_1$.

The primary outcome analyses were performed on an intent to-treat basis. Between-group differences in demographic and clinical variables were assessed using ANOVA and χ^2 tests. Logistic regression analysis, with CGRA uptake (yes/no) as the outcome variable, was employed to compare the treatment effect between TCN versus UC and TP as the primary analysis. Comparison between UC and TP was also performed as a secondary analysis. We also tested the effect of the interventions for those with a self-reported outcome and used both negative and multiple imputation methods to estimate CGRA uptake in

those with an unknown outcome as sensitivity analyses to determine whether the intervention effect estimates were sensitive to imputation and if the conclusions were consistent.

Multiple imputation assumed missing at random and was based on verified CGRA within 6months and demographic information; having a primary care provider; cancer site (breast v ovarian cancer); and number of first- and second-degree relatives with cancer, as well as the a priori interaction of the intervention with potential effect modifiers: race, ethnicity, health insurance status, literacy level, and household income. Ten imputed data sets were generated using IVEware with sequential regression, and Rubin's rule was applied to combine results using SAS Proc Mianalyze. Odds ratios, CGRA percentages, and 95% CIs were conducted using SAS v9.4.

With a final sample size of at least 212 per arm and 3% of CGRA for TP or UC, the minimum detectable OR for comparisons between TCN and TP or between TCN and UC is 1.86 with 80% power and 5% overall type I error rate (2.5% for each comparison) after multiplicity adjustment.

Demographic and clinical characteristics of participants were compared among three arms using ANOVA and chi-square analysis. The mediators at baseline and 1 month were compared (within arms and between arms) using paired *t*-tests and two-sample *t*-tests; CGRA uptake at 6 months was compared using a chi-square test.

Generalized structural equation modeling (GSEM) was used for mediation analysis because CGRA uptake is a binary outcome. All 1-month cognitive and emotional mediators were controlled for baseline levels and all scores were standardized. Maximum likelihood estimation was used for estimating regression coefficients/parameters. Indirect effects were estimated, and a bootstrapping method (1,000 replications) was used to construct 95% confidence intervals.

Age, household income, education attainments, ethnicity, health insurance, urban/rural residence, cancer type, years since diagnosis, health literacy, and family history of cancer were controlled as covariates in all regressions in GSEM. We adopted negative imputation for the outcome variable, CGRA uptake – assuming no documentation meant no uptake. Sensitivity analyses with multiple imputation for missing data were conducted, based on the assumption of missing at random. Effect estimates were derived using Rubin's rule. All analyses were performed using Strata MP 17. The Monte Carlo simulation technique, was used to examine the power and estimate the minimal detectable indirect effects. Results showed that our study has at least 80% power ($\alpha = 0.05$, two-sided) to test a minimal indirect effect of 0.37 for a single mediator and an indirect effect of 0.007-0.032 for serial mediation with two to three mediators.

An intent-to-treat principle was followed in the analysis. Demographic and clinical characteristics of participants were compared across the 3 arms using ANOVA and χ^2 analysis. Logistic regression analysis was employed to compare the medically verified CGRA uptake (yes/ no) at 12months between TCN vs UC and TP; a binary intervention variable (TCN vs TP; TCN vs UC) was added to logistic models separately. Negative outcome imputation and multiple imputation were then used as sensitivity analyses to determine whether the intervention effect estimates were sensitive to imputation and if the conclusions were consistent. Negative outcome imputation assumed that CGRA did not occur if there was no documented verification. Multiple imputation was based on verified CGRA within 12months and demographic and clinical variables. Twenty-five imputed datasets were used to provide a combined estimate for missing values based on Rubin's rule, using Proc MI and Proc MIANALYZE in SAS v9.4. To estimate the cumulative probability of medically verified CGRA uptake following the intervention to 12-month follow-up, Kaplan-Meier estimates were calculated along with the 95% confidence intervals for each study arm. Participants were censored if they were lost to follow-up, or the event did not occur within the 12- month follow-up. All tests of statistical significance were 2-sided.

Analysis includes costs that would be incurred while implementing this intervention in a clinical practice for 212 patients (the number of patients in the TCN arm). Costs of intervention development and study-specific costs were excluded; we excluded costs of participant ascertainment and recruitment, participants' compensation, and survey administration.

The costs include the following sources: (1) training health coaches, (2) brochure printing and mailing, (3) staff costs consisting of salaries and overhead for administrative staff and health coaches, (4) participant time, and (5) downstream genetic counseling and testing and related costs. Costs were calculated in 2022 dollars from a societal perspective.

Most costs were assumed to be variable (ie, costs rise with an increased number of participants), whereas training costs were considered fixed. Our base case analysis uses the number of patients from the study to assess variable costs. In an additional scenario analysis, we increased the number of patients.

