1.0 Research Design

1.1 Purpose/Specific Aims

The primary purpose of this study is to compare the effectiveness of a usual care (UC) vs. targeted generic print (TP) vs. tailored telephone counseling and navigation intervention (TCN) on cancer genetic risk assessment (CGRA) uptake at 6 months for hereditary breast and ovarian cancer (HBOC). Secondary purposes are: 1) to compare the effectiveness of a TP vs. a TCN intervention vs. UC on CGRA uptake at 12 months, after removal of key access barriers; 2) to compare uptake of genetic testing for HBOC across the three study arms at 6 and 12 months; 3) to compare cognitive (beliefs, attitudes, and knowledge) and affective (distress, stress, fear) intermediate endpoints among women in the three study arms and explore potential underlying theoretical mediating and moderating mechanisms that will further specify and elucidate significant intervention effects; and 4) to perform an economic evaluation alongside this randomized controlled trial to estimate the cost effectiveness of the two interventions compared to each other and usual care, for uptake of CGRA services from the societal and payer perspectives.

The New Jersey State Cancer Registry (NJSCR) will collaborate with investigators from the state cancer registries of Colorado and New Mexico ([name] = overall Principal Investigator) to identify women recently diagnosed with high-risk breast and ovarian cancer. The NJSCR will (a) recruit and consent New Jersey patients who are eligible to participate in the study, and (b) securely send contact and cancer-related information to the overall PI for women who consent so that they can be enrolled onto study by the overall PI. This application is for case ascertainment using the NJCSR.

A. Objectives

AIM 1: Compare the effectiveness of a TP vs. a TCN intervention vs. UC on CGRA uptake 6 months (primary outcome) after the intervention and at 12 months, after removal of key access barriers.

AIM 2: Compare uptake of genetic testing for HBOC across the three study arms at 6 and 12 months.

AIM 3: Compare cognitive (beliefs, attitudes, and knowledge) and affective (distress, stress, fear) intermediate endpoints among women in the three study arms and explore potential underlying theoretical mediating and moderating mechanisms that will further specify and elucidate significant intervention effects.

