1.6 Study Variables

A. Independent Variables, Interventions, or Predictor Variables

Intervention Arms. Following completion of the baseline survey, participants will be randomly assigned to 1 of 3 study arms: 1) a Usual Care (UC) control arm; 2) a mailed Targeted Print arm (TP); and 3) Tailored Counseling & Navigation (TCN) arm. We hypothesize that the TCN intervention will increase CGRA uptake significantly compared to UC and the TP intervention.

Arm 1- Usual Care: A usual care arm is included to assess GGRA uptake in the absence of intervention as well as priming from the surveys for the primary outcome analysis.

Arm 2- Mailed Targeted Print: Participants randomized to this arm will be mailed an educational brochure within two weeks of completing the baseline survey. The brochure will be available in English and Spanish. It addresses important evidence-based theoretical targets: CGRA guideline (knowledge), threat appraisal (to validate or raise risk perceptions, HBOC seriousness), response efficacy (benefits and expectations about CGRA), self-efficacy messages (CGRA resources, insurance reimbursement, assistance for those with financial challenges), and possible actions to take (make an appointment and discuss with provider). As described in Section D.1, both the targeted print and tailored intervention materials (described below) were developed using formative community engaged research methods.¹¹⁹

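### SAP item 1 tests mediation of CGRA intentions in the TCN arm alone with time as the exposure, so a mediator that moves equally in usual care can still be declared established, and P_M is not a share of the TCN vs UC effect

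*SAP*

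**What the plan says.** SAP item 1 first compares the arms. Logistic regression compares one-month intentions, and a mixed model assesses "between-treatment-arm and pre-to-post-differences in the scores for CGRA intentions and each theorized mediator variable". It then moves to mediation, giving as its reason: "Due to the significant improvement in CGRA intentions for TCN compared to the other study arms". From there the analysis stays inside one arm: "we studied the mediational relationships for CGRA intentions in TCN using the within-group analysis".

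Three models are fitted, each with a person-level intercept and a 0/1 time variable (baseline, one month):

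- Model 1.1: intentions on time, coefficient c1.
- Model 1.2: mediator on time, coefficient a1.
- Model 1.3: intentions on time and mediator, mediator coefficient b2.

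The null hypothesis is a1·b2 = 0. When the 95% interval excludes 0, the SAP considers that it has "established the mediation relationship". It then adds a percentage: "The percentage of indirect effect for significant theoretical intervention variables was calculated as" P_M = a1·b2/c1.

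The Protocol's Aim 3 (section 1.1) is to "explore potential underlying theoretical mediating and moderating mechanisms that will further specify and elucidate significant intervention effects".

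**The concern.** Aim 3 asks how the intervention works, and the reason given for the mediation analysis is a between-arm result. The models then drop the randomised comparison. In a single arm, a1 is how far the mediator moved in TCN for any reason, including repeated questioning, the passage of time and regression to the mean, and c1 is the same kind of quantity for intentions. Neither has the change in UC subtracted.

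The entry condition does not repair this. It requires intentions to improve more in TCN than in the other arms, but it places no condition on the mediators. A direct effect of TCN on intentions is enough to satisfy it, and any belief that drifted in every arm can then be named as a mechanism of TCN with a percentage attached. Readers choosing which counseling components to keep would be misdirected.

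Change without intervention is plausible here. Protocol section 1.6.A gives as one purpose of the UC arm to capture "priming from the surveys for the primary outcome analysis". That sentence concerns uptake rather than beliefs, so it is context only.

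**Working it through.** The documents give no figure for this analysis, so there is none to reproduce. The check is algebra first, then illustrative rates.

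**Algebra.** Let the mediator change by d in both TCN and UC, let b be the mediator-to-intention slope, and let TCN have a direct effect g on intentions.

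- TCN vs UC effect on the mediator: d − d = 0, so the between-arm indirect effect is 0 × b = 0.
- SAP test quantity: a1·b2 = d·b, non-zero whenever d and b are non-zero.
- SAP ratio: P_M = d·b/(g + d·b).
- TCN vs UC effect on intentions: (g + d·b) − d·b = g, none of it through the mediator.

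With d = 0.3, b = 0.3, g = 0.4: a1·b2 = 0.09, c1 = 0.49, P_M = 0.09/0.49 = 18%. The between-arm effect is 0.40, with 0% mediated.

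**Inputs for the rates.** The figure of 212 per arm comes from the power statement in SAP item 2; item 1 states no sample size. Everything else is assumed: SD of change 1, b = 0.3, g = 0.4 SD, the same mediator drift in all three arms, and no extra mediator change in TCN. Entry requires TCN to exceed both UC and TP on intention change, each at p < 0.05. Each scenario used 3,000 simulated three-arm trials, change scores (equivalent to person intercepts with two time points) and a Monte Carlo interval for the product.

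| Equal drift (SD) | Entry condition met | Met, and mediation declared (TCN only) | Between-arm version declares |
|---|---|---|---|
| 0 | 96.5% | 4.6% | 5.0% |
| 0.1 | 96.7% | 30.1% | 4.8% |
| 0.2 | 97.4% | 80.1% | 4.8% |
| 0.3 | 97.2% | 96.0% | 5.5% |

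**Hand check.** The standard error of a1 is 1/√212 = 0.0687. Drifts of 0.1, 0.2 and 0.3 give z = 1.46, 2.91 and 4.37, so a1 is significant with probability about 0.31, 0.83 and 0.99. Multiplying by the entry probabilities gives about 0.30, 0.81 and 0.96, in line with the table.

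**Sensitivity.** Over g = 0.3–0.5 and b = 0.3–0.4, the TCN-only declaration rate is 25–30% at drift 0.1, 66–84% at 0.2 and 77–99% at 0.3. The between-arm version stays at 4–6%. Median P_M at drift 0.3 runs from 15% to 28%.

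A second set of assumptions (g = 0.3, b = 0.2–0.5, within-person correlation 0.5, no entry condition applied) gives 21–34%, 65–85% and 83–99% at 212 per arm. With 170 per arm (about 80% of 212, the Protocol's retention figure) it gives 17–26%, 50–75% and 71–96%.

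**When some mediation is real.** P_M still overstates the between-arm share. With drift 0.2 everywhere plus 0.2 extra in TCN, P_M = (0.4 × 0.3)/(0.4 + 0.4 × 0.3) = 0.12/0.52 = 23%, while the between-arm share is (0.2 × 0.3)/(0.4 + 0.2 × 0.3) = 0.06/0.46 = 13%. With 0.3 extra the figures are 0.15/0.55 = 27% and 0.09/0.49 = 18%.

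**Could another analysis supply the missing step?** The item 1 mixed model and the between-arm mediator tests in item 3 could reveal an equal change in UC, but neither enters the rule or P_M. The structural equation model in item 3 has 6-month uptake as its outcome, not intentions.

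**The case against.** The SAP labels the analysis as within-group and never says that P_M is a share of the TCN vs UC effect. On its own terms the null hypothesis is false when drift and slope are both non-zero, so the 30%, 80% and 96% are not type I error rates of the stated test. That is correct. They measure how often the stated rule would name a mechanism that has no between-arm component. The labelling does not rescue the inference, because the section is justified by the between-arm result and concludes that mediation is established.

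Item 1 already contains the between-arm mediator contrast. If the TCN vs UC contrast were also required, the declaration rate in the base case would fall to 1.5–4.6%. This stands as a lighter remedy for false mechanisms, but it leaves P_M as a within-TCN ratio, and the SAP does not make the link.

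The rates rest wholly on assumed inputs. Exactly equal drift is a limiting case for an intervention built to shift these beliefs, and at 0.1 SD the problem is moderate. Only the single-mediator step was simulated, not the simultaneous one. All of this stands and limits the size of the problem, not the algebra.

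Finally, the Protocol's mediation plan in section 6.1.A centres on 6- and 12-month effects, and the one-month intentions analysis is exploratory. That bears on severity only.

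**Conclusion.** The concern holds. As written, the rule does not test whether a mediator carries the effect of TCN relative to UC or TP, and P_M cannot be read as a share of that effect. This follows from the model equations and needs no assumption about size.

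How often it would mislead depends on drift that the documents do not report. Under the assumptions listed, the rate runs from about a quarter to a third of trials at 0.1 SD up to 77–99% at 0.3 SD, against 4–6% for a between-arm version. A declaration also requires a non-zero mediator-to-intention slope, so it is likely rather than certain. The analysis should be corrected, but it serves a secondary, exploratory aim and the primary outcome is untouched.

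**What to change.** Fit the models on all three arms with arm, time and arm-by-time:

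- Take the a path as the arm-by-time effect on the mediator, for TCN vs UC and for TCN vs TP.
- Take the b path from the intention model that includes arm-by-time and the within-person mediator.
- Express the percentage mediated relative to the arm-by-time effect on intentions.
- Report the TCN-only result as a descriptive within-arm association, next to the between-arm mediator contrast, and drop the claim that mediation is established.

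The cost is a re-analysis of data already collected and revised SAP wording. Intervals widen because the standard error of the a path rises from 1/√212 = 0.069 to √(2/212) = 0.097. Under the same inputs, a true extra mediator change of 0.3 SD in TCN is detected in 87–88% of trials (99% or more with the TCN-only rule), and 0.2 SD in 51–55% (82–99%). The b path remains non-randomised under either version, and the report should say so.

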All recruitment materials, surveys, and intervention materials will be available to participants in English or Spanish, depending on their preference. The TCN session will be conducted in English or Spanish, depending on the participant's preference. Spanish materials will be submitted to the IRB after the English materials have been approved. To further facilitate communication, Spanish speaking participants and study staff may use over the phone translation services.

There will be 4 surveys over the course of the study period (baseline, 1 m, 6m, 12 m) and will include different components as described below. These are developed at the prime site.

CGRA Decision and Genetic Test Uptake: Participants who have CGRA within 6 months of the intervention (or baseline survey for UC arm) will be considered “completers” of CGRA for the primary outcome. The primary outcome is medical record verified CGRA delivered by the 6-month follow-up. Those reporting that they had CGRA will be asked to sign a medical release form so that we may verify their self-reported CGRA. This approach is extremely feasible and has been successful in ours^{41,134} and others^{135,136} prior work. We will track the type of provider (e.g., physician, genetic counselor, etc.) who provided CGRA and document their genetics training via the documentation form. Using the same strategy, we will assess CGRA utilization at 12 months. Through the medical record release signed by patients, self-reported genetic testing (including type of test and test result) will also be medical record verified at 6 and 12 months.

Sociocultural Factors and Cues to Action: 1) Sociodemographics: age, gender, education, household income, financial status, marital status, rural-urban community area code,¹³⁷ living biological children, and health insurance status, country of origin, years lived in the U.S; 2) Medical history: personal/family history of cancer, cancer stage, health status, co-morbidity index; 3) Acculturation: Short Acculturation Scale;¹³⁸ 4) Family and friends social support and encouragement to obtain CGRA;^{41,139,140} 5) Family orientation: The Familism Scale;¹⁴¹ 6) Brief Fatalism Scale;^{142,143} 7) Health System Distrust;¹⁴⁴ 8) Receipt of a physician/provider recommendation for CGRA; and 9) Primary health care provider received tailored letter in the TPN arm.

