Physician/Health Care Provider Recommendation and Communication	x	x	x	x	Will assess whether healthcare providers have discussed participant's risk of HBOC and CGRA, and how participants feel discussing CGRA and genetic testing with health care provider.
Cancer Genetic Risk Assessment (Genetic Counseling)		x	x	x	Participants will be asked whether they have had CGRA, the provider who conducted the CGRA, and the provider's genetics training. CGRA will be medical record verified.
Cancer Genetic Risk Assessment Intention	x	x	x	x	One item will measure future intention to get cancer genetic risk assessment. In follow up surveys, this will only be asked if participant does not report uptake of CGRA
HBOC Genetic Testing Uptake		x	x	x	Participants will be asked whether they have had HBOC genetic testing, what type of genetic test they had, and the facility where the testing was done. Genetic testing will be medical record verified.
HBOC Genetic Testing Intention	x	x	x	x	One item will measure future intention to get genetic testing for HBOC. In follow up surveys, this will only be asked if participant does not report uptake of genetic testing.
Decisional conflict for CGRA: SURE Scale ^{153,154} ($\alpha = 0.86$)		x	x	x	Decisional conflict associated with the CGRA decision will be measured separately with 4 items using the SURE Scale ^{153,154}
Decisional conflict for HBOC genetic testing: Low Literacy Decisional Conflict Scale (DCS)SURE Scale ^{153,154} ($\alpha = 0.86$)			x	x	Decisional conflict associated with the HBOC gene test decision will be measured separately with 4 items using the SURE SCALE ^{153,154}
Decisional satisfaction with CGRA: Satisfaction with Decision Instrument ^{155,156} ($\alpha = 0.90$).			x	x	Decisional satisfaction will be assessed using the Satisfaction with Decision Instrument. ^{155,156} Four questions assess their personal satisfaction with their decision and three additional items assess

					how they feel about their CGRA decision in relation to their family.
Decision Regret Scale ¹⁵⁸ ($\alpha = 0.81-0.92$)			x	x	Five items will ask about regret regarding the decision to have or not have CGRA. ¹⁵⁸
CGRa and HBOC Genetic Testing Facilitators ^{42,126}	x	x	x	x	Facilitators include but are not limited to: help from family, desire to reduce risk of second cancers, and help/referrals from medical professionals.

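### The listed imputation predictors omit self-reported CGRA and intention, so imputed uptake is too low if women who reported CGRA without a record are classed as unknown

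*SAP*

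**What the plan says.** **How the outcome becomes known.** The primary outcome is CGRA confirmed in the medical record by 6 months. Under Study Instruments in protocol Section 1.8, verification starts from the woman's own report: "Those reporting that they had CGRA will be asked to sign a medical release form". A woman can therefore report CGRA and have no record, because she gave no release or the record was not obtained.

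**What else is collected.** Table 5 of the protocol schedules self-reported CGRA at 1, 6 and 12 months. It also schedules intention at baseline, 1, 6 and 12 months: "One item will measure future intention to get cancer genetic risk assessment". At follow-up the intention item is put only to women who have not reported uptake.

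**6-month sensitivity analyses (SAP item 2).** There are three. One uses self-report: "We also tested the effect of the interventions for those with a self-reported outcome". The other two, negative and multiple imputation, estimate uptake in "those with an unknown outcome as sensitivity analyses to determine whether the intervention effect estimates were sensitive to imputation". The imputation model rests on a missing-at-random assumption, and the SAP states that it "was based on verified CGRA within 6months and demographic information". The other predictors listed are whether the woman has a primary care provider, her cancer site, and how many of her relatives had cancer. Arm enters through one further clause: "as well as the a priori interaction of the intervention with potential effect modifiers". The modifiers are race, ethnicity, insurance, literacy and income. Neither self-report nor intention appears.

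**12-month sensitivity analyses (SAP item 4).** These are negative imputation and a multiple imputation described only by verified CGRA within 12 months and demographic and clinical variables. No self-report analysis is listed.

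**Missing not at random.** Protocol Section 6.1.A promised sensitivity analyses for this case. SAP items 2 and 4 name no such model.

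**The concern.** Only women who say yes can end up as reporters without a record. If they are in the unknown group, whether the outcome is missing depends on a variable that the imputation model does not use, so missing at random given the listed predictors is implausible for them. The model cannot tell such a woman from one who was lost to follow-up, and gives both about the arm's average probability. For a woman who has said that she had CGRA, that is far too low.

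At stake are the imputed uptake percentages and differences and, if verification succeeded more often in one arm, the odds ratio as well. The TCN arm has extra staff contact and navigation, so equal verification should be shown rather than assumed.

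**Working it through.** The plan gives no figure on this point to reproduce. The check computes what the listed model would be expected to return.

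**Inputs**
- True uptake U: 34% in TCN and 7% in UC, the planning values in protocol Section 6.1.B.
- Share of self-reports that can be verified, v: assumed 80%, range 70% to 90%.
- Share of self-reports that are true, t: assumed 90%, range 80% to 100%.
- Every woman who had CGRA reports it, reporters without a record count as unknown, and loss to follow-up is at random. Such loss does not alter the expected imputed rate.

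**Step 1: equal verification in both arms**

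Share reporting CGRA: s = U/t. Known yes: s × v × t = U × v. Known outcomes: 1 − s(1 − v). A model without self-report imputes every unknown at q = Uv / [1 − s(1 − v)], which is then also the completed-data estimate.

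- TCN: s = 0.34/0.9 = 0.3778; q = 0.272 / (1 − 0.0756) = 29.4%.
- UC: s = 0.07/0.9 = 0.0778; q = 0.056 / (1 − 0.0156) = 5.7%.

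| Method | TCN | UC | Difference (points) |
|---|---|---|---|
| Truth | 34.0% | 7.0% | 27.0 |
| Multiple imputation as listed | 29.4% | 5.7% | 23.7 |
| Negative imputation (Uv) | 27.2% | 5.6% | 21.6 |
| Self-report at face value (s) | 37.8% | 7.8% | 30.0 |
| Multiple imputation using self-report | 34.0% | 7.0% | 27.0 |

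The last row imputes unverified reporters at t: 0.272 + 0.3778 × 0.2 × 0.9 = 0.34, and 0.056 + 0.0778 × 0.2 × 0.9 = 0.07. The negative-imputation row leaves out loss to follow-up, which would lower it further.

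Over the assumed ranges, the difference under the listed model runs from 21.5 points (v = 70%, t = 100%) to 25.6 points (v = 90%, t = 80%). The odds ratio stays between 6.84 and 7.08, against a true (0.34/0.66)/(0.07/0.93) = 6.84.

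**Step 2: verification differs by arm**

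With accurate self-report (t = 100%), the imputed odds in each arm are Uv/(1 − U). The imputed odds ratio is therefore the true one multiplied by v(TCN)/v(UC).

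| v in TCN | v in UC | Imputed uptake | Difference (points) | Odds ratio |
|---|---|---|---|---|
| 0.8 | 0.8 | 29.2% vs 5.7% | 23.5 | 6.84 |
| 0.9 | 0.6 | 31.7% vs 4.3% | 27.4 | 6.84 × 1.5 = 10.27 |
| 0.6 | 0.9 | 23.6% vs 6.3% | 17.3 | 6.84 × 0.667 = 4.56 |

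As the middle row shows, the difference can slightly exceed the true 27.0 although both percentages are too low.

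**Step 3: what intention can add**

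A woman who has already reported CGRA at 1 month is not asked the 1-month intention item, so only her baseline answer exists. Intention can help mainly for women who had not yet reported uptake, including those lost later.

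**The case against.** The strongest reply is that SAP item 2 already analyses self-report separately. If that analysis counts reporters as events, as its wording suggests, it treats a reporter without a record as yes, while negative imputation treats her as no. Together they roughly bracket these women at 6 months. This stands, and it rules out the inference that the 6-month sensitivity analyses as a whole repeat the bias.

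The bracket does not replace a better model. Taken at face value, self-report overshoots when some reports are wrong (30.0 points in the illustration), and it covers only women who answered. It is also not listed at 12 months.

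Other points that stand:
- The SAP does not define an unknown outcome. A reporter without a record could be unknown, a no, or handled only in the self-report analysis. The imputation argument applies to the first reading.
- The primary analysis is a logistic regression, and equal verification leaves its odds ratio essentially unbiased.
- The values for v and t are assumptions, and 7% is the protocol's planning rate, whereas SAP item 2 uses 3% for TP or UC. At 3% the mechanism is the same: with v between 0.6 and 0.9 and accurate self-report, the imputed probability is 1.8% to 2.7%.
- A reader might infer that cost per added CGRA is overstated. Protocol Section 6.1.A puts a difference in effectiveness in the denominator, but neither it nor SAP item 5 says that imputed percentages are used, so the link is not shown.
- Adding self-report is not free of difficulty. Releases are sought only from reporters, so a self-reported no almost perfectly predicts a non-event.

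**Conclusion.** The point holds as a weakness of the imputation models, conditional on reporters without a record being classed as unknown. In that case imputed uptake is too low in each arm. With equal verification, the illustration loses about 3 points of a 27-point difference (range 21.5 to 25.6 points retained). At 12 months, on the same condition, both listed imputation methods understate uptake in these women, with no self-report analysis to set against them.

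Two stronger readings are not supported. The documents do not show that the treatment odds ratio is biased: that needs verification to differ by arm, and no rate is given, so both size and direction are unknown. Nor do they show that the difference in uptake is always understated, since it can err either way when verification is unequal.

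**What to change.** 1. Define an unknown outcome explicitly, and include in it women who reported CGRA but have no record.
2. Add self-reported CGRA status (yes, no, not answered) at the surveys up to each endpoint to both the 6-month and the 12-month imputation models. Add baseline intention and, where it was asked, 1-month intention.
3. Report the verification rate among reporters by arm at 6 and 12 months, so that readers can judge whether the odds ratio is exposed.

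This is a cheap improvement. The variables are already scheduled for collection, and SAP item 1 already analyses 1-month intention. The SAP is written in the past tense, so the cost is a rerun of the imputations. Near-perfect prediction by a self-reported no must also be handled, for example by penalised or augmented imputation. Little gain should be expected from intention in women who had already reported uptake.
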